8.1 Definitions

Unanticipated Problems Involving Risk to Subjects or Others (UPIRTSO)

Any unanticipated problem or adverse event that meets the following three criteria:

- Serious: Serious problems or events that results in significant harm, (which may be physical, psychological, financial, social, economic, or legal) or increased risk for the subject or others (including individuals who are not research subjects). These include: (1) death; (2) life threatening adverse experience; (3) hospitalization inpatient, new, or prolonged; (4) disability/incapacity persistent or significant; (5) birth defect/anomaly; (6) breach of confidentiality and (7) other problems, events, or new information (i.e. publications, DSMB reports, interim findings, product labeling change) that in the opinion of the local investigator may adversely affect the rights, safety, or welfare of the subjects or others, or substantially compromise the research data, **AND**
- Unanticipated: (i.e. unexpected) problems or events are those that are not already described as potential risks in the protocol, consent document, not listed in the IB, or not part of an underlying disease. A problem or event is "unanticipated" when it was unforeseeable at the time of its occurrence. A problem or event is "unanticipated" when it occurs at an increased frequency or at an increased severity than expected, AND
- Related: A problem or event is "related" if it is possibly related to the research procedures.

Adverse Event

An untoward or undesirable experience associated with the use of a medical product (i.e. drug, device, biologic) in a patient or research subject.

Serious Adverse Event

Adverse events are classified as serious or non-serious. Serious problems/events can be well defined and include;

- death
- life threatening adverse experience
- hospitalization
- inpatient, new, or prolonged; disability/incapacity
- persistent or significant birth defect/anomaly

and/or per protocol may be problems/events that in the opinion of the sponsor-investigator may have adversely affected the rights, safety, or welfare of the subjects or others, or substantially compromised the research data.

All adverse events that do not meet any of the criteria for serious, should be regarded as **non-serious adverse events**.

Adverse Event Reporting Period

For this study, the study treatment follow-up period is defined as 18 months following the topical application of PRP at the time of RP.

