Preexisting Condition

A preexisting condition is one that is present at the start of the study. A preexisting condition should be recorded as an adverse event if the frequency, intensity, or the character of the condition worsens during the study period.

General Physical Examination Findings

At screening, any clinically significant abnormality should be recorded as a preexisting condition. At the end of the study, any new clinically significant findings/abnormalities that meet the definition of an AE must also be recorded and documented as an AE.

Post-study Adverse Event

All unresolved AEs should be followed by the sponsor-investigator until the events are resolved, the subject is lost to follow-up, or the AE is otherwise explained. At the last scheduled visit, the sponsor-investigator should instruct each subject to report, to the sponsor-investigator, any subsequent event(s) that the subject, or the subject's personal physician, believes might reasonably be related to participation in this study.

Abnormal Laboratory Values

A clinical laboratory abnormality should be documented as an AE if the serum hemoglobin on postoperative day 2 is <8 g/dL. If hemoglobin level is considered an AE, then patient should have hemoglobin monitored and if there is a downward trend or if clinical symptoms are associated with the value then blood transfusion should be considered.

Hospitalization, Prolonged Hospitalization or Surgery

Any AE that results in rehospitalization or prolonged hospitalization (greater than 1 week) should be documented and reported as a serious AE unless specifically instructed otherwise in this protocol. Any condition requiring surgery should be documented as an AE if the condition meets the criteria for an AE.

Neither the condition, hospitalization, prolonged hospitalization, nor surgery are reported as an AE in the following circumstances:

- The planned hospitalization for RP.
- The prolonged hospitalization for diagnosis not related specifically to RP.
- Surgical procedure not related to RP.

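### Two stated rules, the 8.1 exclusions keyed to RP and the removal of withdrawn men, can take events out of the primary safety count

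*Combined protocol and SAP*

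**What the plan says.** **Exclusions from AE reporting.** Under the hospitalization and surgery heading of protocol section 8.1: "Neither the condition, hospitalization, prolonged hospitalization, nor surgery are reported as an AE in the following circumstances". Three circumstances follow. The first is the planned RP admission. The other two are "The prolonged hospitalization for diagnosis not related specifically to RP" and "Surgical procedure not related to RP".

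**Other text in 8.1.** An adverse event is defined as "An untoward or undesirable experience associated with the use of a medical product". Just above the exclusions, 8.1 says "Any condition requiring surgery should be documented as an AE if the condition meets the criteria for an AE".

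**Serious prolonged stays.** The seriousness list in 8.1 has hospitalization followed by "inpatient, new, or prolonged; disability/incapacity", with no minimum length. The later rule reads "Any AE that results in rehospitalization or prolonged hospitalization (greater than 1 week) should be documented and reported as a serious AE", and then makes an exception for cases where the protocol specifically instructs otherwise.

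**Recording.** The Study Summary says that all events are collected, and section 8.2 requires every adverse event in the study period to be recorded. The worksheet in 8.3.1 has a field for relationship to the research, which separates drug, surgery and other intervention.

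**Withdrawn men.** Section 4.4.1 allows withdrawal during surgery (for example for blood loss above 750 mL) and after RP. Section 4.4.2 leaves withdrawn men's data out of the analysis. Section 4.4.3 removes and replaces them until 20 complete 18 months. Section 7.3 evaluates consented men who complete postoperative visits.

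**The concern.** The two contested exclusions ask whether a stay or operation is related to RP. RP is the background operation that every man has. Section 1.5 places the risks of taking part in the blood collection and in the effects of PRP, and the primary objective concerns PRP. An event can therefore be possibly related to a study exposure, be judged not RP-related, and not be reported as an AE. The exclusion also covers the underlying condition, so the loss is not limited to the label on the stay or operation.

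The removal of withdrawn men acts on the same count by another route. A man who has had the draw, or the draw and PRP, has been exposed. If he leaves, his events leave the analysis with him and a replacement takes his place in the denominator. If men leave because of how they fared, the remaining count is biased towards safety.

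**Working it through.** The plan gives no event rate, withdrawal rate or safety threshold, and 7.1 does not derive the sample size of 20 from a formula. No figure of the plan can be reproduced, so the check is mainly a comparison of text.

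**Step 1: which rule governs an event possibly due to the draw or PRP?**

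| Place | Rule |
|---|---|
| 8.1, AE definition | It is an AE if associated with the product |
| 8.1, condition requiring surgery | It is an AE if it meets the AE criteria |
| 8.1, exclusions | It is not reported as an AE if it is a prolonged stay or surgery judged unrelated to RP |
| 8.2 and Study Summary | All are recorded and collected |

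The rule on serious stays yields to specific instructions elsewhere, so the exclusions can be read as overriding that one sentence. Nothing states whether they also override 8.2, the AE definition or the sentence on surgery.

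**Step 2: when is relatedness to the research judged?** Section 8.3 has the worksheet completed once an AE has been identified. An event that an exclusion says is not an AE may never reach the 8.3.1 relationship field.

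**Step 3: who is exposed but not analysed?** Section 5.4.1 has the blood drawn during RP, and PRP applied only after the anastomosis and hemostasis. Withdrawal for blood loss is decided during surgery. The documents do not fix the order of the draw and that decision, so a man can be drawn and then withdrawn. Section 1.5 links the draw itself to reduced blood volume and possible transfusion. A man who received PRP and later withdraws is removed as well.

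**Step 4: scale only.** The one-sided exact 95% upper bound for x events in n men is the 0.95 quantile of Beta(x + 1, n − x). For x = 0 this reduces to 1 − 0.05^(1/n), which with n = 20 is 1 − 0.05^(1/20) = 13.9%.

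| Men with an event | Proportion | Upper bound |
|---|---|---|
| 0/20 | 0% | 13.9% |
| 1/20 | 5% | 21.6% |
| 2/20 | 10% | 28.3% |
| 1/21 | 4.8% | 20.7% |

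An event lost through the exclusions turns 1/20 into 0/20, or 2/20 into 1/20. One exposed man who has an event, withdraws and is replaced turns 1/21 into 0/20. These are hypothetical counts, not estimates.

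**Step 5: prolonged stays.** A stay prolonged by a week or less falls within the seriousness list on its face, but is not named by the later rule. Two readers could class it differently.

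**The case against.** The strongest reply is that the exclusions will seldom apply. The draw and the PRP application are both steps within the operation, and section 1.5 has the blood taken from sites needed for the anesthetic. Most of their complications would naturally be called RP-related. A needle-site infection meets an exclusion only if it also prolongs the stay or needs surgery. Growth of residual tissue would be sought through serum PSA at five visits from week 12 to month 18, whatever its AE label. The Study Summary also has perioperative complications, length of stay and transfusion evaluated in all patients. The UPIRTSO test in 8.1 refers to the research procedures, and FDA reporting in 8.3.2 turns on a causal link to the study drug.

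This stands as a limit on size. It does not remove the point: those data are not counted as AEs, and the UPIRTSO and FDA routes mainly concern unanticipated or unexpected serious events, whereas the risks in 1.5 are already described.

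A reader might infer more than the text supports:
- **That readmissions are excluded.** Rehospitalization without surgery is in neither contested exclusion, and 8.1 makes an AE that causes it serious.
- **That the one-week wording is a flat contradiction.** The seriousness list does not define prolonged, and every man is already in hospital for RP, so the later wording can be read as supplying the definition. The text does not say that it does.
- **That events before PRP are not collected**, because follow-up is "18 months following the topical application of PRP at the time of RP". That phrase sets the length of follow-up. Section 6.2 and the schedule in 6.8 already assess AEs at the surgery visit.

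It is also fair to say that removing withdrawn men is a separate rule from the exclusions. It belongs here because it acts on the same count.

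**Conclusion.** The point holds in a limited form and should be fixed. The exclusions use RP as their reference, conflict with the AE definition, the sentence on surgery, the Study Summary and 8.2, and can act before relatedness to the research is judged. The text supports saying that such events can drop out. It does not show that complications of the draw or PRP are excluded as a class, or that many would be lost. The removal of exposed men who withdraw is explicit in 4.4.2 and 4.4.3.

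The size of any undercount cannot be computed from the documents. The illustration of 1/20 becoming 0/20 assumes one lost event. The plan is descriptive with no safety threshold, so the bounds are tied to no planned decision. The case of a man drawn and then withdrawn in surgery assumes that the draw comes before the decision to withdraw him, which the protocol allows but does not specify. The one-week wording is a secondary matter of clarity.

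**What to change.** 1. In 8.1, delete the two exclusions that refer to RP, or reword them so that no event possibly related to the blood draw, the device or PRP is excluded. Keep the exclusion for the planned RP admission. Judge relatedness with the existing 8.3.1 worksheet field.
2. In 4.4.2, 4.4.3 and 7.3, define a safety population of every man who had the study blood draw, whether or not he received PRP or later withdrew, with that number as the denominator. Keep the 20-completer cohort for the functional outcomes only.
3. Reconcile the two places in 8.1 so that one definition of a serious prolonged stay applies.

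These are wording changes. The worksheet field and the AE review at the surgery visit already exist, and 4.4.2 says that withdrawn men still have routine postoperative monitoring. The cost is that a few more unrelated background events will be listed.

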8.2 Recording of Adverse Events

At each contact with the subject, the study team must seek information on AE by specific questioning and, as appropriate, by examination. Information on all adverse events should be recorded immediately in the source document, and also in the appropriate AE section of an electronic adverse event worksheet. All clearly related signs, symptoms, and abnormal diagnostic, laboratory or procedure results should recorded in the document.

All adverse events occurring during the study period must be recorded. The clinical course of each event should be followed until resolution, stabilization, or until it has been ultimately determined that the study treatment or participation is not the probable cause. Serious adverse

events that are still ongoing at the end of the study period must be followed up, to determine the final outcome. Any serious AE that occurs after the study period and is considered to be at least possibly related to the study treatment or study participation should be recorded and reported immediately.

8.3 Reporting of Serious Adverse Events and Unanticipated Problems

When an AE has been identified, the study team will take appropriated action necessary to protect the study participant and then complete the Study Adverse Event Worksheet form and log. The sponsor-investigator will evaluate the AE and determine the necessary follow-up and reporting required.

8.3.1 Sponsor-Investigator reporting: notifying the Mayo IRB

For any SAE, an AE worksheet will be sent to the IRB. In this situation the PI and study coordinators will document the data related to the SAE on the event worksheet and notify the IRB using the standard reporting procedure. The sponsor-investigator will specifically report to the Mayo IRB any UPIRTSOs and Non-UPIRTSOs according to the Mayo IRB Policy and Procedures.

Information collected on the adverse event worksheet (and entered in the research database):

- Subject's name:
- Medical record number:
- The date the adverse event occurred:
- Description of the adverse event:
- Relationship of the adverse event to the research (drug, surgery, or other intervention):
- If the adverse event was expected:
- The severity of the AE: (use a table to define severity scale 1-5)
- If any intervention was necessary:
- Resolution: (was the incident resolved spontaneously, or after discontinuing treatment)
- Date of Resolution:

8.3.2 Sponsor-Investigator reporting: Notifying the FDA

The sponsor-investigator will report to the FDA all unexpected, serious suspected adverse events and reactions according to the required safety reporting timelines, formats and requirements.

Unexpected fatal or life threatening suspected adverse reactions where there is evidence to suggest a causal relationship between the study drug/placebo and the AE, will be reported as a serious suspected adverse reaction. This will be reported to the FDA by telephone or by fax using FDA Form 3500A, no later than 5 calendar days after the sponsor-investigator's initial receipt of the information about the event and the report will also be made in writing within 10 days as required under 21 CFR 812.150.

Other unexpected serious suspected adverse reactions where there is evidence to suggest a causal relationship between the study drug/placebo and the adverse event, will be reported as a serious suspected adverse reaction. This will be reported to the FDA on FDA Form 3500A, no later than

15 calendar days after the sponsor-investigator's initial receipt of the information about the event.

Any clinically important increase in the rate of serious suspected adverse reactions over those listed in the protocol or product insert will be reported as a serious suspected adverse reaction. This will be reported to the FDA on FDA Form 3500A no later than 15 calendar days after the sponsor-investigator's initial receipt of the information about the event.

Findings from other studies in human or animals that suggest a significant risk in humans exposed to the drug will be reported. This will be reported to the FDA on FDA Form 3500A, no later than 15 calendar days after the sponsor-investigators initial receipt of the information about the event.

8.4 Unmasking/Unblinding Procedures

Not applicable

8.5 Stopping Rules

Not applicable

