1.4 Clinical Data to Date

To date, there is no available clinical research data on use of PRP application to the NVB intraoperatively at the time of nerve-sparing RP. Clinical application of PRP using a similar topical application, however, has been found to be safe and efficacious for a variety of musculoskeletal indications including osteoarthritis, chronic tendinopathy, nerve injury and ligamentous injuries.⁵⁻¹⁰

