Platelets contain growth factors and the hypothesis of the study is that the growth factors will augment healing of the NVB after surgery. There is a possibility that the growth factors could cause adverse healing of the NVB. There is also a possibility that if residual prostate tissue is present that growth of the tissue could occur. There is a low risk that if the residual prostate tissue were cancerous that the growth factors could contribute to a higher chance of cancer recurrence. The relatively short term effect (<4 hours) of PRP applied topically will significantly decrease the risk of promoting growth of prostate tissue. It is also defined approximately 15-20% of men undergoing radical prostatectomy can expect to have recurrence after surgery. Based on the physiology of growth factors, it is thought the risk of PRP independently increasing risk of prostate cancer recurrence is very unlikely.

Benefits are thought to outweigh the risks of the study. Topical application of autologous PRP at the time of RP will permit supraphysiologic doses of growth factors to be present on the NVB. The growth factors may help promote healing and/or decrease the surgical trauma associated with RP. This may augment healing and recovery of erectile function after RP as measured during the 18 month study duration. Subjects will be asked to complete questionnaires regarding urological symptoms, quality of life (urinary control and ED) before and at 3, 6, 9, 12, and 18 months following the procedure.

2 Study Objectives

Primary Objective: To evaluate the safety and tolerability of using platelet rich plasma on the NVB after nerve-sparing radical prostatectomy.

Secondary Objective(s):

- To assess the feasibility of applying 1 dose of PRP intra-operatively at the time of bilateral nerve-sparing RP in 20 men with prostatic adenocarcinoma.
- To assess preliminary clinical benefit/efficacy of using PRP in facilitating early nerve healing and decreasing ED at 3, 6, 9, 12 and 18 months after nerve-sparing RP. To assess change in urological function by measuring urinary control before and at 3, 6, 9, 12 and 18 months after PRP treatment during nerve sparing surgery.

3 Study Design

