3.1 General Design

This is an open label, human study evaluating the safety and tolerability, feasibility, and efficacy, s of PRP applied in topical fashion intra-operatively during RP. Subjects will be screened at outpatient clinic visit appointments and interested qualified subjects will be

consented and offered participation in this trial. The study aims to enroll 20 men with newly diagnosed prostatic adenocarcinoma that are planning to undergo bilateral nerve-sparing RP. Once written consent has been obtained baseline functional and laboratory assessments will be obtained and patients will be followed for the expected duration for study participation of 18 months.

Since the present study is a single-arm study, evaluation of safety and efficacy parameters will have to be performed using benchmark outcomes from historical controls. At Mayo Clinic, all patients undergoing RP are included in the Mayo Clinic Prostatectomy Registry. The prostatectomy registry is prospectively maintained by study nurses. The prostatectomy registry maintains detailed oncologic and quality of life data using PSA testing and the same validated questionnaires proposed by the current study. The comparator for the present study would be other subjects from the Mayo Clinic Prostatectomy Registry that underwent bilateral nervesparing RP within the same study dates and met all of the other inclusion and exclusion criteria for the present study but did not have PRP applied intraoperatively to the neurovascular bundles.

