Since we meet all of the criteria established in part 1271.10 and also meet exception criteria listed in part 1271.15, we believe that the PRP created in this study would be solely regulated

under section 361 of the Public Health Safety Act and that regulation of the created product as a drug under section 351 of the Public Health Service Act would not apply. Accordingly, the need to pursue an IND application for the proposed use was not felt to be applicable. However, upon request for an exemption from IND regulations, FDA subsequently decided to regulate this study under an Investigational Device Exemption, (IDE) for the investigational use of an approved blood separation device.

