8.6 Medical Monitoring

It is the responsibility of the PI to oversee the safety of the study at his/her site. This safety monitoring will include careful assessment and appropriate reporting of adverse events as noted above, as well as the construction and implementation of a site data and safety-monitoring plan (see section 10 "Study Monitoring, Auditing, and Inspecting"). Medical monitoring will include a regular assessment of the number and type of serious adverse events.

Since the present study is a single-arm study, evaluation of safety and efficacy parameters will also be performed using benchmark outcomes from historical controls. At Mayo Clinic, all patients undergoing RP are included in the Mayo Clinic Prostatectomy Registry. The prostatectomy registry is prospectively maintained by study nurses. The prostatectomy registry maintains detailed oncologic and quality of life data using PSA testing and using the same validated questionnaires proposed by the current study. By using other subjects from the Mayo Clinic Prostatectomy Registry that underwent bilateral nerve-sparing RP within the same study dates (and those that met all of the other inclusion and exclusion criteria for the present study but did not have PRP applied intraoperatively to the neurovascular bundles), another means to compare the safety and preliminary evidence of efficacy will be achieved.

9 Data Handling and Record Keeping

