10.1 Study Monitoring Plan

Periodic study monitoring will be provided on behalf of the Sponsor by staff from the Mayo Clinic Office of Research Regulatory Support. Monitoring may include but will not necessarily be limited to review of the study regulatory documents, source data and database entries throughout the duration of the study to help ensure the completeness, validity and integrity of the data. Original signed informed consent forms will be reviewed. Written monitoring reports with findings and recommended and suggested corrective actions will be provided to the sponsor, who will subsequently provide them to the IRB at time of annual continuing review.

The PI, assisted by delegated study staff, will also monitor study conduct and documents. PI and study staff meetings will be held bi-weekly.

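### Section 8.5 sets no stopping rule in a first-use safety study, so nothing in the protocol pauses PRP application, even after a related death

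*Combined protocol and SAP*

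**What the plan says.** The whole content of "8.5 Stopping Rules" is *Not applicable*.

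Section 2 gives the aim: "Primary Objective: To evaluate the safety and tolerability of using platelet rich plasma on the NVB after nerve-sparing radical prostatectomy". Section 1.4 describes the evidence base for this use: "To date, there is no available clinical research data on use of PRP application to the NVB intraoperatively at the time of nerve-sparing RP". It adds that a similar topical use of PRP "has been found to be safe and efficacious for a variety of musculoskeletal indications".

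The rest of the safety text is substantive:

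- 8.3 has the sponsor-investigator evaluate each adverse event.
- 8.3.1 sends a worksheet to the IRB for any SAE.
- 8.3.2 sends unexpected serious suspected reactions to the FDA. Fatal or life-threatening ones go within 5 calendar days.
- 8.6 makes the PI responsible for safety. It requires regular review of the number and type of SAEs and a site data and safety-monitoring plan, for which it points to section 10.
- 10.1 adds that "PI and study staff meetings will be held bi-weekly".
- 5.4 records that "FDA subsequently decided to regulate this study under an Investigational Device Exemption".
- 3.1 says that "evaluation of safety and efficacy parameters will have to be performed using benchmark outcomes from historical controls", and names concurrent registry patients as the comparator.

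**The concern.** A study whose main question is whether an intervention is safe, in a setting with no earlier clinical data, is one in which a stopping or pausing criterion does apply. Section 1.5 itself names possible harms: infection, hypotension or transfusion from the 180 mL draw, adverse healing of the bundle, and growth of residual tissue that might be cancerous.

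Without a trigger, whether and when to pause is decided after the event by the people running the study, or by the IRB or FDA once they have been told. Meanwhile the next scheduled man may receive PRP. What is at stake is the exposure of men operated on between a serious related event and the end of its review. The IRB also has no pausing criterion to assess in advance.

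**Working it through.** The plan gives no boundary, error rate or expected SAE rate, and 7.1 justifies the 20 men by what is usual for such trials. There is no figure to reproduce. The check is therefore a reading of every place where a pause could be written, followed by the behaviour of the proposed trigger.

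**Step 1. Does any other text pause PRP at study level?**

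| Place | What it triggers |
|---|---|
| 4.4.1 | Withdraws one man in theatre for blood loss above 750 mL or advanced disease; a single-patient criterion, not a response to harm from PRP |
| 8.1, laboratory values | Hemoglobin below 8 g/dL on day 2 is an adverse event; leads to monitoring and possibly transfusion |
| 8.3 | Protective action for the participant concerned, then evaluation and reporting |
| 8.3.1 | Report to the IRB |
| 8.3.2 | Report to the FDA at 5, 10 or 15 days; a clinically important rise in the rate of serious suspected reactions also leads only to a report |
| 8.6 | Regular SAE review, registry comparison, site plan (see section 10) |
| 10.1 | Document and data monitoring, staff meetings |

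None names an event or count at which PRP application pauses. A DSMB appears only in the abbreviation list and as an example inside a definition in 8.1.

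**Step 2. Could the registry supply a benchmark rate?** 8.6 says the registry "maintains detailed oncologic and quality of life data using PSA testing" and the study's questionnaires. That description does not include related-SAE rates, so every rate below is an assumption.

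**Step 3. How often would a severity trigger fire?** Let q be the chance per man of a death or life-threatening event judged at least possibly related. With n men, P(at least one pause) = 1 − (1 − q)^n.

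| q (assumed) | n = 20 | n = 24 (4 extra men, assumed) |
|---|---|---|
| 0.1% | 1 − 0.999^20 = 2.0% | 1 − 0.999^24 = 2.4% |
| 0.5% | 1 − 0.995^20 = 9.5% | 1 − 0.995^24 = 11.3% |
| 1% | 1 − 0.99^20 = 18.2% | 1 − 0.99^24 = 21.4% |

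The second column matters because 4.4.3 replaces withdrawn men until 20 complete, so more than 20 may have the draw.

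**Step 4. What would an added count rule do?** Take a pause at the r-th early related SAE in 20 men: P(X ≥ r), with X binomial(20, p) and p assumed.

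| p | r = 2 | r = 3 | r = 4 |
|---|---|---|---|
| 5% | 26.4% | 7.5% | 1.6% |
| 10% | 60.8% | 32.3% | 13.3% |
| 20% | 93.1% | 79.4% | 58.9% |
| 30% | 99.2% | 96.5% | 89.3% |

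For r = 3, suppose each event is known before the next man is treated and the pause ends PRP use. The mean number treated is then 19.6, 18.1, 13.6 and 9.9. Multiplying by p gives 0.98, 1.8, 2.7 and 3.0 men with an event, against 1, 2, 4 and 6 with no rule. The saving is almost nil at 5–10% and appears only at rates for which the documents give no support.

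**The case against.** The strongest reply is that this is a 20-man study of an autologous product, given once, made with an FDA-cleared device and run under an IDE, with PRP reported as safe in musculoskeletal uses. A formal statistical boundary is not obligatory. Every SAE already reaches the IRB, so review would happen anyway. All of that stands, and it argues for a light rule. It does not supply the missing link between an event and a halt in exposure.

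A second reply is that the site plan called for in 8.6 may be a separate document, and that IRB or IDE conditions may contain pause criteria. That also stands. A reader might infer that no such criteria exist anywhere, or that the study would carry on after a related death. The documents show neither. They show only that the protocol does not say, and that section 10, where 8.6 sends the reader, does not say either.

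A third reply is that the PRP-specific harms named in 1.5, poor nerve healing and recurrence, appear too late for a rule on early events to limit exposure. This is correct. Against a background recurrence of 15–20% (1.5), a pause rule is not the tool for that harm, and the point does not claim it is.

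**Conclusion.** The point holds in a narrow form. 8.5 declares stopping rules inapplicable where they do apply, and no other protocol text pauses PRP after any event. What a trigger adds is an automatic halt while the already required review runs. Judgement of relatedness remains.

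A reader might go further and conclude that safety oversight is absent, or that a particular count boundary is required. The first is contradicted by 8.3, 8.6 and 10.1. The second is unsupported. Without a related-SAE rate in the documents, the count threshold only trades false pauses against missed harm: at r = 3, a 7.5% chance of pausing if the true rate is 5%, and a 20.6% chance (100 − 79.4) of missing a 20% rate.

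The severity trigger needs no such rate to justify it. Its pause probabilities (2.0%, 9.5%, 18.2% in 20 men) rest on assumed values of q and on independence between men.

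**What to change.** Replace *Not applicable* in 8.5 with:

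> PRP application pauses pending IRB review after any death or life-threatening event at least possibly related to PRP or the study blood draw. Every man who had the draw counts, including those withdrawn in theatre or later, and replacements.

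In 4.4.2, state that such events are still captured for men withdrawn after the draw. At present that section describes only routine postoperative monitoring for them and leaves their data out of the analysis. If pause criteria already exist in the site plan or in IRB or IDE conditions, cite them in 8.5.

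Optionally, add a count of early related SAEs, for example a pause at the third, with the pause probabilities printed beside it. The sponsor and IRB should choose the threshold.

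The cost is two short edits. For men who stay in the study no new data are needed, because the 8.3.1 worksheet already records relationship and severity. For withdrawn men, continued capture of these events is a small addition. During a pause, scheduled men have RP without PRP and are replaced. Accrual and review time are not in the documents. Assuming 1 to 2 men a month and 1 to 2 months of review, a pause affects 1 × 1 = 1 to 2 × 2 = 4 men. At q = 0.5% that is an expected 0.095 × 1 ≈ 0.1 to 0.095 × 4 ≈ 0.4 men over the study, counting one pause.
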